3.3. DOSING

3.3.1. Dosing Regimen

The dosing regimen will be a single dose treatment injection of RZL-012 in multiple sites.

Six subjects in cohort 1, all assigned to the RZL-012 treatment group will be dosed at a maximal dose of 40 mg RZL-012 (approximately 1/6.25th the NOAEL as determined in the GLP toxicology study). Dosing will be calculated according to the size of the nodule (diameter) as determined by ultrasound in a dose of 5mg/cm²:

Nodule of 2-2.9cm diameter, as determined by ultrasound, will be injected 2 injections (0.1 mL each, 1 cm apart); total of 10 mg RZL-012.

Nodules of 3-3.9cm diameter, as determined by ultrasound, will be injected 3 injections (0.1 mL each, 1 cm apart); total of 15 mg RZL-012.

Nodules of 4-8cm diameter, as determined by ultrasound, will be injected 4 injections (0.1 mL each, 1 cm apart); total of 20 mg RZL-012.

Cohort 1 – Dercum's disease			
Number of Subjects – Active	6		
Nodule size – diameter (cm)	2-2.9	3-3.9	4-8
Total Dose of RZL-012 (mg)	10	15	20
Dose per NOAEL*	1/25 th	1/18.75 th	1/12.5 th
Number of Injections	2	3	4

Six subjects in cohort 2, all assigned to the RZL-012 treatment group, will be dosed as follows:

The first 3 subjects will receive 30mg RZL-012 in 6 injections (0.1mL each) in one leg followed by 30mg RZL-012 (6 injections, 0.1mL each) in the second leg adding up to 12 injections of 60mg RZL-012 (1/4.688th the NOAEL based on HED from GLP toxicology study).

The last 3 subjects will receive 40mg RZL-012 in 8 injections (0.1mL each) in one leg followed by 40mg RZL-012 (8 injections, 0.1mL each) in the second leg adding up to 16 injections of 80mg RZL-012 (1/3.125th the NOAEL based on HED from GLP toxicology study).

*based on HED from GLP toxicology

Cohort 2 - Lipedema		
Number of Subjects – Active	2	2
Total Dose RZL-012 (mg)	60	80
Dose per NOAEL*	1/4.688	1/3.125
Number of Injections	12	16

Dosing of subjects in each cohort will progress consecutively from one individual to the other at 7-day intervals. This study design will allow the physicians to monitor safety for at least 7 days prior to dosing the next subject. For cohort 2 the decision to proceed to the next dose level will be made after reviewing all safety data collected by Day 14 within 2 ± 1 d of the last dosed subject. The trial will proceed within a cohort provided that no more than one subject experiences intolerable side effects in a cohort, and based on the decision made by the Principal Investigator (PI) and the Medical Monitor.

3.3.2. Intolerable Side Effect

An intolerable side effect defined as any of the following treatment-related adverse drug reactions (ADRs):

Any Grade 3 or greater event except for the following (For the following events, a discussion will be held by the PI and the Medical Monitor to decide whether considered as an intolerable side effects):

- Flu-like symptoms and fever that responds to standard treatment within 72 hours
- Localized edema and erythema
- Pruritus
- Pain
- Skin/soft tissue inflammation
- Fat Atrophy
- Liver enzymes abnormality
- Non-significant lab abnormalities, lasting less than 7 days

To establish a threshold for clinical abnormalities and liver enzyme abnormalities the following tables were formed for main expected side effects. For the following abnormalities, associated with the injection site or treatment intolerable side effect would be any Grade 3 or greater event:

Clinical Abnormalities Table

* Erythema – the measured local reaction at the greatest single diameter beyond the injected area surface of all injections (For Dercum's disease – nodules of 2-2.9 cm diameter 2*2 cm, nodules of 3-3.9 cm diameter 3*2 cm nodules of 4-8 cm diameter 4*2 cm. For lipedema -12*2 cm for the first subjects, 15*2cm for the following subjects and 16*2cm for the last subjects), the measurement should be recorded as a continuous variable.

Local Reaction to Injectable Product	Mild (Grade 1)	Moderate (Grade 2)	Severe (Grade 3)	Potentially Life Threatening (Grade 4)
Pain	Does not interfere with activity Repeated use of non-narcotic pain reliever > 24 hours	Interferes with activity	Any use of narcotic pain reliever beyond 7 days following injection or prevents daily activity	Emergency room (ER) visit or hospitalization
Tenderness	Discomfort to touch or with movement	Significant discomfort at rest	Prevents daily activity	ER visit or hospitalization
Erythema/Redness*	2.5 - 7 cm	7.1 - 15 cm	> 15 cm	Necrosis or exfoliative dermatitis
Induration/Swelling**	2.5 - 7 cm and does not interfere with activity	7.1 - 15 cm or interferes with activity	>15 cm or prevents daily activity	Necrosis

**Induration — the measured local reaction at the greatest single diameter beyond the injected area surface of all injections (For Dercum's disease – nodules of 2-2.9 cm diameter 2*2 cm, nodules of 3-3.9 cm diameter 3*2 cm nodules of 4-8 cm diameter 4*2 cm. For lipedema -12*2 cm for the first subjects, 15*2cm for the following subjects and 16*2cm for the last subjects), the measurement should be recorded as a continuous variable.

Liver Enzyme Abnormalities Table

Serum *	Mild (Grade 1)	Moderate (Grade 2)	Severe (Grade 3)	Potentially Life Threatening (Grade 4)
Liver Function Tests –ALT, AST increase by factor	3 x ULN	3 – 5 x ULN	5-10 x ULN beyond 10 days	> 10 x ULN beyond 10 days

Study discontinuation is to be considered by the investigator in any case of an intolerable side effect and the actions taken are to be fully documented in source documents and Case Report Forms (CRFs).

To be considered an intolerable side effect, such an event must be considered to be possibly or probably related to the study drug.

Subjects experiencing an intolerable side effect will be withdrawn from the study, but followed for toxicity.

The study may also be prematurely terminated in any of the following cases:

- Recurring serious or severe ADR clinically evaluated by PI as warranting study termination.
- A decision made by Sponsor and/or IRBEC and/or local regulatory agency to terminate the study.

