
Intolerable Side Effect Definition
	
An intolerable side effect defined as any of the following treatment-related adverse drug reactions (ADRs):
 
 • Any Grade 3 or greater event except for the following (For the following events, a discussion will be held by the PI and the Medical Monitor to decide whether considered as an intolerable side effects): 
 ○ Flu-like symptoms and fever that responds to standard treatment within 72 hours ○ Localized edema and erythema ○ Pruritus ○ Pain ○ Skin/soft tissue inflammation ○ Fat Atrophy ○ Liver enzymes abnormality ○ Non-significant lab abnormalities, lasting less than 7 days (See Section 3.3.2) 
Subjects experiencing an intolerable side effect will be withdrawn from the study, but followed until the event resolves or becomes stable; all actions taken are to be fully documented in source documents and Case Report Forms (CRFs). To be considered an intolerable side effect, such an event must be considered to be possibly or probably related to the study drug
 
The study may also be prematurely terminated in any of the following cases:
 
 • Recurring serious or severe ADR clinically evaluated by PI as warranting study termination. • A decision made by Sponsor and/or Institutional Review Board (IRB)/Ethics Committee (EC) and/or local regulatory agency to terminate the study. 																								

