--	---

	
 - For Dercum's disease subjects – ultrasound assessing nodules size (diameter) and quality. - For lipedema subjects – measurement of leg circumference above the knee and assessing fat thickness and nodular quality by ultrasound. - Subjects will be questioned for AEs.

Safety Analysis
	
Safety data from the study will be summarized descriptively by treatment and cohort. Descriptive statistics will be calculated for quantitative data and frequency counts and percentages will be provided for categorical data. The nature, frequency, seriousness, severity and relation to study drug of AEs will be tabulated for all subjects combined and by treatment. Change-from-baseline values for vital signs, clinical laboratory and ECG will be summarized. Shift tables of normal / abnormal versus baseline may be presented as well. Draize scores will be presented in tabular format by visit, treatment, and cohort. Serious adverse events (SAEs) will be described in narratives as part of the study report.

Study Endpoints
	
Primary Endpoint: Evaluation of the overall safety of RZL-012 injection into the subcutaneous fat in Dercum's disease and lipedema. The primary safety endpoint is the incidence of intolerable side effects.
 
Secondary Endpoints:
 
 1. For lipedema subjects - The reduction in local subcutaneous fat in the injection site region as compared to baseline based on ultrasound (reduction in nodules size and/or numbers) and leg circumference above the knee assessments. 2. For Dercum's disease subjects - The reduction in local subcutaneous fat in the injection site region as compared to baseline based on ultrasound (reduction in nodules size and/or numbers). 3. Extended duration of the fat reduction effect. To that end, ultrasound images and above the knee circumference measurement will be followed for 56 days. 4. Elucidation of the tissue changes by ultrasound of the injection site to include reduction in fat thickness and nodular quality. 5. Improvement in local pain as measured by Comparative Pain Scale and by the reduction in the use of analgesics. 6. Improvement in QOL and function in lipedema subjects as measured by questionnaire (such as The Lower Extremity Functional Scale (LEFS)).

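### Section 3.3.2 gives two incompatible rules on whether Grade 3 or greater pain, edema/erythema and liver enzyme events count toward the primary safety endpoint

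*Protocol*

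**What the plan says.** Protocol 3.3.2 defines an intolerable side effect as a treatment-related reaction of Grade 3 or greater, with a list of exceptions. For the listed types, "a discussion will be held by the PI and the Medical Monitor to decide whether considered as an intolerable side effects". The list includes pain, localized edema and erythema, and liver enzyme abnormality. The synopsis carries the same list.

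Two grading tables follow in 3.3.2, introduced by this sentence: "For the following abnormalities, associated with the injection site or treatment intolerable side effect would be any Grade 3 or greater event". The first table is headed "Local Reaction to Injectable Product" and has rows for pain, tenderness, erythema and induration/swelling. The second grades ALT and AST. Under either rule, "such an event must be considered to be possibly or probably related to the study drug".

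The classification feeds the main result. The synopsis states: "The primary safety endpoint is the incidence of intolerable side effects". Protocol 10.2.1 adds AEs to that endpoint. Protocol 10.5.4 and SAP 5.8.13 report the incidence overall and by cohort with an exact 95% interval. Protocol 3.3.1 and 4.1 let a cohort continue only while at most one of its subjects is affected; 3.3.1 also requires a decision by the investigator and the Medical Monitor.

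The Grade 3 pain cell reads: "Any use of narcotic pain reliever beyond 7 days following injection or prevents daily activity". Exclusion criterion 3 excuses a positive drug screen when the drug is prescribed, opiates are on that screen (6.1.9.3), and 7.1 bars chronic NSAIDs and aspirin but not opioids.

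**The concern.** The list and the tables cover the same kinds of event and prescribe different outcomes. One rule makes the outcome a case-by-case judgement; the other makes it automatic. With six subjects per cohort, a single classification changes the primary count visibly and decides whether the cohort has any tolerance left. The study is open label, so if the rule is unsettled, it will be chosen after the event and the subject are known.

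The events concerned are not remote. Section 3.3.2 describes the tabulated abnormalities as the main expected ones, and Section 7.2 lists injection-site erythema, edema and pain, and transient ALT/AST rises, from phase 0. Section 3.2 gives 20 mg as the highest phase 0 dose and plans 60 and 80 mg in lipedema.

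**Working it through.** **Step 1. The two rules side by side**, for a related event of Grade 3 or greater:

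| Event | On the exception list? | In the tables? | Outcome by the list | Outcome by the tables |
|---|---|---|---|---|
| Pain | yes | yes | discussion | intolerable |
| Erythema | yes | yes | discussion | intolerable |
| Induration/swelling | yes, read as localized edema | yes | discussion | intolerable |
| ALT/AST rise | yes, as liver enzymes | yes | discussion | intolerable |
| Tenderness | not by name | yes | intolerable (general rule) | intolerable |

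Four of the five tabulated abnormalities get conflicting answers.

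**Step 2. Does any text rank the rules?** The synopsis carries only the list and, at its laboratory item, refers back to 3.3.2. Section 9.2 grades AEs by CTCAE v4.03 and does not mention the conflict. The SAP plans a frequency table (14.4.1-2) but gives no definition. No sentence settles it.

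**Step 3. Grade 4.** Both rules apply to Grade 3 or greater, so the conflict reaches Grade 4: an emergency room visit or hospitalization for pain, necrosis in the erythema and swelling rows, and ALT/AST above 10 times ULN lasting more than 10 days.

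**Step 4. Effect on the primary result.** The plan states no event rate or precision figure to reproduce; the sample size is a six-per-group convention (Protocol 10.3). The inputs are n = 6 per cohort and n = 12 overall, with the exact (Clopper-Pearson) 95% interval:

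- x = 0: lower limit 0, upper limit 1 − 0.025^(1/n). For n = 6 this is 1 − 0.5407 = 45.9%; for n = 12 it is 1 − 0.7354 = 26.5%.
- x = 1: lower limit 1 − 0.975^(1/n), which is 0.4% for n = 6 and 0.2% for n = 12. The upper limit p solves (1 − p)^n + n·p·(1 − p)^(n−1) = 0.025, giving 64.1% and 38.5%.

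| Disputed event | Cohort | Overall |
|---|---|---|
| Not counted | 0/6 = 0% (0% to 45.9%) | 0/12 = 0% (0% to 26.5%) |
| Counted | 1/6 = 17% (0.4% to 64.1%) | 1/12 = 8% (0.2% to 38.5%) |

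If a cohort already has one undisputed event, the disputed one leaves it at 1/6, where it may continue, or takes it to 2/6 = 33% (4.3% to 77.7%), where the rule fails.

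**Step 5. The pain cell.** Take a subject on a prescribed opioid at an unchanged dose who has mild, drug-related pain at the injection site after Day 7. Entry is allowed. The pain is new, so it is an AE (9.1.1). It is local and related, so it belongs in the table. It does not interfere with activity, which is Grade 1 wording. The unchanged opioid also satisfies the first half of the Grade 3 cell. No tie-break is written; taking the highest grade met gives Grade 3.

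**The case against.** **The rules can be reconciled.** Section 3.3.2 says the tables were drawn up to set a threshold, and they add duration limits of their own: narcotics past 7 days, ALT/AST past 10 days. One could read a two-tier scheme: an expected event that is Grade 3 on CTCAE goes to discussion, and one that also crosses the table threshold is intolerable. Or the tables might only set the grade that triggers the discussion. Both readings are possible, and they give opposite outcomes for the same table Grade 3 event. Neither is spelled out, and the sentence above the tables is unconditional. This supports asking for one rule; it does not remove the conflict.

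**The consequence is limited.** Safety analysis is descriptive, 10.2.1 includes AEs in the primary endpoint, and the event appears in the AE tables and listings either way. Continuation also rests on the judgement of the investigator and the Medical Monitor. Any single event shifts a proportion by this much when n = 6. All of this stands and limits the weight of the point. The one-subject limit and the headline incidence still need a settled count.

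**The pain cell is narrower than it looks.** A reader might infer that background opioid use as such becomes a Grade 3 event. The documents do not support that. The table covers local reactions, relatedness is required, unchanged pre-existing pain is not an AE, causality weighs concomitant medication (9.3), and 6.1.15 has findings judged against baseline medical data for grading as well as identification. What survives is the single case in Step 5, and that case meets the Grade 1 wording too.

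**Conclusion.** The conflict is real and worth correcting. For Grade 3 or greater pain, localized edema or erythema, and liver enzyme events, 3.3.2 both defers the decision and makes it, with no order of precedence. One such event counts as 0 or 1: 0/6 (0% to 46%) or 1/6 (0.4% to 64%) in a cohort, and within or against the one-subject limit. These figures assume a related event and a full cohort of six.

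The pain cell is a minor wording point. The documents give no opioid prevalence, so no frequency can be attached to it, and nothing in them suggests that it would stop a cohort.

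A reader might also infer from phase 0 that the conflict is likely to arise, because one subject had a severe ALT rise. The documents do not support a probability. Section 1.2.4 gives neither the treatment arm nor the multiple of ULN, and says the rise resolved within 14 days. It may not have met the requirement of more than 10 days; if it did not, the table would not grade it 3 and the two rules would not collide.

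**What to change.** 1. Replace the sentence above the tables in 3.3.2 with:

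> The tables below set the grade for these abnormalities. A Grade 3 event of a type listed above goes to the PI/Medical Monitor discussion, with the decision documented before the next subject is dosed. Any Grade 4 event (including necrosis, ER visit or hospitalization) and any other Grade 3 or greater event is an intolerable side effect.

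Align the exception list in 3.3.2 and the synopsis with it. The relatedness requirement stays. Counting Grade 4 outright matters: sending all listed events to discussion would make necrosis or hospitalization discretionary at 60 to 80 mg.

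If the sponsor intends the tables as bright lines, delete pain, localized edema and erythema, and liver enzymes from the list in both places instead. That choice belongs to the sponsor.

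2. Optionally, limit the narcotic clause to new use, or an increase over the recorded pre-injection dose, for injection-site pain beyond 7 days, and keep the alternative for pain that prevents daily activity.

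Cost: one sentence, an aligned list and, optionally, one table cell. No new data are needed: dose and reason for use are recorded from one month before entry (6.1.3), and an analgesic diary starts at Screening (6.1.5). The pre-injection diary may cover as little as 2 days, and it lapses between Day 28 and the week before Day 56, so the medication record has to fill the gaps. The main downside of item 2 is that background opioids may mask local pain, which the daily-activity clause only partly covers. Some events will reach Grade 3 only after the next subject has been dosed, because the narcotic and enzyme criteria run past 7 and 10 days; those decisions should be documented before the following dosing.

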6.1.15. Adverse Events

The information obtained during weekly subjects questioning, review of subject's compliance record, physical examinations, vital signs measurements, blood testing, and by any other means will be evaluated in light of baseline medical data and thus provide the basis for adverse events identification and grading.

The trial will proceed within a cohort and from one cohort to the next as long as no more than one subject experiences intolerable side effects and based on the decision made by the PI. Proceeding from one subject to the next will be based on the decision made after reviewing all safety data collected by Day 7 within 2 ± 1 d of the last dosed subject in each cohort.

The AEs reported during the trial will be graded (see Section 9), documented, and assessed in light of their clinical significance and relation to investigational product. In addition, the following information regarding the AE must be obtained: AE description, start date, end date (if applicable) or ongoing, severity, seriousness, relationship to study drug, outcome (e.g., resolved / unresolved), and action taken (e.g., concomitant medication). The sponsor or the sponsor representative will provide information regarding serious adverse event (SAE) expectedness based on data included in the IB. AE monitoring will be conducted throughout subject's participation up to 56 days after injection.

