9.2. ADVERSE EVENT GRADING

AE will be documented and graded according to the National Cancer Institute Common Terminology Criteria for Adverse Events (CTCAE) v4.03 June 14, 2010) (10).

AE that do not appear in the CTCAE will be graded as follows:

- Mild (Grade 1): Sign or symptom, usually transient, requiring no special treatment and generally not interfering with usual activities.
- Moderate (Grade 2): Sign or symptom, which may be ameliorated by simple therapeutic measures, may interfere with usual activity.
- Severe (Grade 3): Sign or symptom that is intense or debilitating and that interferes with usual activities and/or requires hospitalization. Recovery is usually aided by therapeutic measures and the discontinuation of the study product may be required.
- Life-threatening or disabling (Grade 4): Sign or symptom that is life-threatening or disabling.
- Death (Grade 5): Death related to AE

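### ALT/AST above 5 x ULN has no grade in the liver table until an unanchored 10-day condition is met, so the automatic threshold is out of reach at the Day 7 review and may be at the Day 14 escalation review

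*Protocol*

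**What the plan says.** All references are to the Protocol unless stated.

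- **Liver table (3.3.2).** Grade 2 for ALT/AST covers 3 to 5 x ULN with no time condition. Grade 3 is "5-10 x ULN beyond 10 days". Grade 4 is above 10 x ULN with the same 10-day condition. Neither cell says from when the days are counted.
- **Role of the table (3.3.2).** "For the following abnormalities, associated with the injection site or treatment intolerable side effect would be any Grade 3 or greater event".
- **Discussion clause (3.3.2).** Liver enzyme abnormality is also on the list of events excepted from the general Grade 3 rule, for which "a discussion will be held by the PI and the Medical Monitor to decide whether considered as an intolerable side effects".
- **Two styles of time limit in the same section.** The pain row counts from injection: "Any use of narcotic pain reliever beyond 7 days following injection or prevents daily activity". The laboratory exception counts duration: "Non-significant lab abnormalities, lasting less than 7 days".
- **Reviews.** Section 6.1.15: "Proceeding from one subject to the next will be based on the decision made after reviewing all safety data collected by Day 7". Section 3.3.1, for Cohort 2: "the decision to proceed to the next dose level will be made after reviewing all safety data collected by Day 14". Dosing within a cohort goes on if no more than one subject has an intolerable side effect and the PI and Medical Monitor agree.
- **General grading (9.2).** "AE will be documented and graded according to the National Cancer Institute Common Terminology Criteria for Adverse Events (CTCAE) v4.03".
- **Endpoint (10.5.4; SAP 5.8.13).** Incidence of intolerable side effects, overall and by cohort, with an exact 95% interval.

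**The concern.** The table is meant to set the liver threshold, yet it grades 4 x ULN immediately and gives 12 x ULN no grade at all until time has passed. The progression reviews take place at or before the point when that time could have passed.

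The signal is not hypothetical. Section 1.2.4 reports a severe ALT rise with a moderate AST rise in one phase 0 subject, seen 14 days after injection and resolved within 14 days, and no other clinically significant systemic event. The top dose there was 20 mg. Here it is 80 mg, four times as much. A repeat of that pattern is the case the table handles worst. On one reading of the 10 days it would be Grade 3 or 4 at the Day 14 review, and on the other it would have no table grade.

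Three things depend on the answer: whether the subject counts toward the limit of one, whether the subject is withdrawn under 3.3.2, and the primary incidence figure.

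**Working it through.** The plan gives no figure to reproduce. The check is day arithmetic, followed by the effect of counting or not counting one event.

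**Inputs**

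- Chemistry after injection: 24 h ± 2 h, then Days 3, 7, 14 and 28 (6.1.9.2).
- Visit window: ± 1 day for Days 0 to 28 (Synopsis, Visit Schedule). The test times are therefore Day 1 = 0.92 to 1.08, Day 3 = 2 to 4, Day 7 = 6 to 8, Day 14 = 13 to 15 and Day 28 = 27 to 29.
- Condition: more than 10 days, read either as (a) days since injection or (b) days since the rise was first detected.

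**Formulas**

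- Reading (a): time = day of the latest test.
- Reading (b): duration = day of latest test − day first seen. Minimum = earliest latest test − latest first test. Maximum = latest latest test − earliest first test.

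**Day 7 review, last-dosed subject**

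- Reading (a): at most 8 days, so not met.
- Reading (b), first seen Day 1: 7 − 1 = 6 days, range 6 − 1.08 = 4.9 to 8 − 0.92 = 7.1, so not met.
- Reading (b), first seen Day 3: 7 − 3 = 4 days, range 6 − 4 = 2 to 8 − 2 = 6, so not met.
- Reading (b), first seen Day 7: 0 days, so not met.

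**Day 14 review, last-dosed subject**

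On reading (a) the time is 13 to 15 days, so any value above 5 x ULN at that visit is Grade 3 or 4. On reading (b):

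| First seen | Nominal days | Range with windows | Beyond 10 days? |
|---|---|---|---|
| Day 1 | 14 − 1 = 13 | 13 − 1.08 = 11.9 to 15 − 0.92 = 14.1 | Yes |
| Day 3 | 14 − 3 = 11 | 13 − 4 = 9 to 15 − 2 = 13 | Depends on visit dates |
| Day 7 | 14 − 7 = 7 | 13 − 8 = 5 to 15 − 6 = 9 | No |
| Day 14 | 0 | 0 | No |

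For the last two rows the next scheduled chemistry is Day 28 (28 − 7 = 21 and 28 − 14 = 14 days), after the decision.

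**Phase 0 pattern.** Suppose a rise is present only at Day 14, with normal tests at Days 7 and 28. It lasted more than 0 and less than 28 − 7 = 21 days (29 − 6 = 23 at the widest windows). Scheduled tests cannot show whether it passed 10 days.

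**One event counted or not** (exact Clopper-Pearson 95% intervals)

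- Cohort: 0/6 = 0% (0 to 45.9%) versus 1/6 = 16.7% (0.4 to 64.1%).
- Overall: 0/12 = 0% (0 to 26.5%) versus 1/12 = 8.3% (0.2 to 38.5%).
- With one other intolerable side effect in the cohort: 1/6, within the limit, versus 2/6 = 33.3% (4.3 to 77.7%), over it.

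These intervals would follow from reclassifying any single event. They show what the endpoint would report and do not measure the flaw itself.

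**The case against.** The strongest reply is that the text can be read coherently. Adverse events are graded under 9.2, a Grade 3 liver event goes to the PI and Medical Monitor, and a persistent one is automatic under the table. On that view the 10 days deliberately spares transient rises, which fits the phase 0 event. This is plausible, but 3.3.2 never says it. It lists liver enzymes as discretionary and then makes table Grade 3 intolerable, without connecting the two.

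A reader might infer that the protocol leaves open which grading scale feeds the count. That goes too far: 3.3.2 gives the table that role. How far the CTCAE would differ for a given value cannot be judged here, because its cut-offs are not in the documents.

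A reader might also infer that early high values are hidden or excluded. The documents do not support that either:

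- Both reviews cover all safety data.
- A physician assesses every out-of-range result (6.1.9).
- Unusual results can be repeated at an unscheduled visit (6.2.7).
- Grade 3 or 4 drug reactions require clinical evaluation and a report to the sponsor within 7 days, and reactions above Grade 1 are followed up (9.5.1).
- Sections 7.3 and 7.4 allow discontinuation or termination.

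The safeguards are real but discretionary, and no criteria are given for the discussion.

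The Day 14 reach is narrow. There is one escalation with three subjects per level. At 7-day spacing, when subject 3 is at Day 14, subject 2 is at Day 14 + 7 = 21 or later and subject 1 at Day 14 + 14 = 28 or later. The claim is therefore confined to the last-dosed subject.

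Finally, the liver table's header carries an asterisk with no matching liver note in the text available. A lost note could supply the anchor and settle the Day 14 reading. An anchor alone would not change the Day 7 result, which holds on both readings.

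**Conclusion.** The point holds and should be fixed, although it is not grounds to halt the trial. For the last-dosed subject, the table's automatic liver threshold cannot be met at the Day 7 review on either reading. Nor can it be met at the 60-to-80 mg Day 14 review if the 10 days is a duration and the rise is first seen at Day 7 or Day 14. What remains is discretion that the section does not tie to the table.

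The effect on decisions is limited. A reader might infer that one unclassified liver event would wrongly let dosing continue. The limit is one subject per cohort, so a single event would not stop dosing even if counted. It changes the count-based result only when the cohort has another intolerable side effect (1 versus 2). The incidence estimate moves by one subject in 6 or in 12, and no success threshold is attached to it.

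Assumptions:

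- The rise is judged possibly or probably related, as 3.3.2 requires.
- Duration is counted from first detection.
- Only scheduled tests are used. If the 2 ± 1 days in the review rules is a lag, an unscheduled draw at its far end with the widest windows could just pass 10 days (8 + 3 = 11 from injection; 18 − 6 = 12 in duration at the Day 14 review). That draw lies outside the data by which each review is defined.
- Cohort 2 follows the three-plus-three scheme of 3.3.1 and the SAP. Section 6.2.3.1 still prints a three-level scheme, which would give two escalation decisions.

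**What to change.** Amend 3.3.2 in three places:

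1. **Grade by level.** ALT/AST of 5 to 10 x ULN is Grade 3 and above 10 x ULN is Grade 4 when observed, with no time condition in the grade.
2. **Separate the grade from the count.** An elevation above 5 x ULN that persists more than 10 days from first detection is automatically an intolerable side effect. An earlier or transient one goes to the PI and Medical Monitor discussion, with a cross-reference between the list and the table.
3. **Add a hold.** If a value above 5 x ULN is unresolved at the Day 7 or Day 14 review, the next dosing or escalation waits and chemistry is repeated promptly under the unscheduled-visit provision. The hold alone neither counts the subject toward the limit nor withdraws the subject.

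This keeps the apparent wish to spare transient rises and makes the rule usable on the day it is needed. The cost is wording in one table and one paragraph, one repeat blood sample when triggered, and an occasional short dosing delay.
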